4.1.1. Inclusion Criteria

OAC indication for atrial fibrillation for a period of at least 12 months following successful PCI with stenting in adult male and female patients ≥ 18 years of age.

Eligibility is assessed 4 hours after sheath removal and within 5 days after successful PCI with stent placement. If a staged PCI is planned, eligibility is assessed after completion of the last stage.

Successful PCI definition:

The success of a PCI procedure is defined by 2 interrelated components: angiographic findings, procedural / clinical outcomes as detailed below:

a) Angiographic Success

A minimum stenosis diameter of $< 20\%$ (as visually assessed by angiography - residual blockage or stenosis reduced to less than 20% of the artery's diameter).

Sufficient enlargement of the lumen at the target site to improve coronary artery blood flow with final TIMI flow grade 3 (visually assessed by angiography), without occlusion of a significant side branch, flow-limiting dissection, distal embolization, or angiographic thrombus.

b) Procedural Success

No major in-hospital clinical complications (e.g. ongoing ISTH major or clinical relevant non-major procedural bleeding at the time of randomization, stroke, emergency CABG).

In summary, a **clinically successful PCI** requires both anatomic and procedural success along with relief of signs and/or symptoms of myocardial ischemia at the time of randomization.

4.1.2. Exclusion Criteria

Subjects who meet any of the following criteria are disqualified from entering the study:

Bleeding risks or systemic conditions

1. Known bleeding diathesis, including but not limited to,
 - a. Uncontrolled active bleeding, encompassing both ISTH major and clinically relevant non-major bleeding, preceding randomization.
 - b. Lesion or condition, if considered to be a significant risk for major bleeding.

This may include but is not limited to: unresolved gastrointestinal ulceration, presence of malignant neoplasms at high risk of bleeding (e.g. malignancies with metastasis), recent unresolved brain or spinal injury, recent brain; spinal or ophthalmic surgery, any intracranial hemorrhage, known or suspected esophageal varices, arteriovenous malformations, vascular aneurysms (of more than 3.5 cm) or major intraspinal or intracerebral vascular abnormalities.

Medication-related

2. INR > 2.5 (the subject can be reconsidered at a later time, but within 5 days of sheath removal).
3. Contraindication to edoxaban, VKA, ASA and/or P2Y₁₂ antagonists;
4. Concomitant treatment with other antithrombotic agents, fibrinolytic therapy and chronic nonsteroidal anti-inflammatory drugs (NSAIDs).

Concomitant conditions and therapies

5. Critically ill or hemodynamically unstable subjects (at the time of randomization) including:
 - a. cardiogenic shock or acute decompensated heart failure, with the requirement for vasopressor agents or inotropic support or mechanical support to support circulation
 - b. respiratory failure requiring endotracheal intubation and mechanical ventilation.
6. Atrial prior mechanical valvular prosthesis;
7. Planned coronary or vascular intervention or major surgery within 12 months; Randomization must be deferred to the last stage in a multistep, multivessel PCI procedure;
8. Moderate or severe mitral stenosis;
9. Ischemic stroke within 2 weeks prior to randomization;

10. Uncontrolled severe hypertension with a systolic blood pressure (BP) ≥ 180 mmHg and/or diastolic BP ≥ 120 mmHg;
 11. End stage renal disease (ESRD) (CrCL < 15 mL/min) or on dialysis;
 12. Known abnormal liver function prior to randomization (incl. hepatic disease or biochemical evidence of significant liver derangement known prior to randomization) (see appendix 17.4).
-

Other exclusion criteria

13. Any of the following abnormal local laboratory results prior to randomization:
 - a. Platelet count $< 50 \times 10^9/L$
 - b. Hemoglobin < 8 g/dL.
14. Unable to provide written TC;
15. Female subjects of childbearing potential without using highly effective contraception (female of childbearing potential is defined as one who has not been postmenopausal for at least one year, or has not been surgically sterilised, or has not had a hysterectomy at least three months prior to the start of this study). Females taking oral contraceptives should have been on therapy for at least three months. Adequate contraceptives include: Combined (estrogen and progestogen containing) oral, intravaginal or transdermal hormonal contraception associated with inhibition of ovulation; progestogen-only oral, injectable or implantable hormonal contraception associated with inhibition of ovulation; intrauterine device (IUD); intrauterine hormone-releasing system (IUS); bilateral tubal occlusion; vasectomized partner; sexual abstinence
16. Pregnant or breast-feeding subjects;
17. Assessment that the subject is not likely to comply with the study procedures or have complete follow-up;
18. Participating in another clinical trial that potentially interferes with the current study;
19. Previous randomization in this study;
20. Active on prescription drug abuse and addiction; abuse of illicit substances (i.e. marijuana; cocaine, methamphetamine heroin) and alcohol abuses during the last 12 months according to the judgement of the investigator
21. Life expectancy < 12 months.

4.2. Screening failures

Subjects are pre-screened based on the information available from the standard care. For subjects fulfilling the pre-screening (i.e., OAC indication for AF for a period of at least 12 months and successful PCI with stenting), IC signature and other study-specific screening procedures take place just prior to randomization. A

subject who withdraws IC before randomization or who fails the inclusion/exclusion criteria before randomization is defined as a screening failure. No further clinical follow-up is performed for these subjects.

4.3. Removal of Subjects From Therapy

4.3.1. Reasons for Withdrawal/Early Discontinuation

The subject is free to withdraw from the study for any reason and at any time without giving reason for doing so and without penalty or prejudice. The Investigator is also free to terminate a subject's involvement in the study at any time if the subject's clinical condition warrants it. It is also possible that the sponsor or the competent authorities request termination of the study if there are concerns about conduct or safety.

Participation of a subject in this clinical study should be discontinued at all periods (except where noted) for any of the following reasons:

1. Withdrawal of Subjects consent at any time of the study
2. Occurrence of any medical condition or circumstance that exposes the subject to substantial risk (including inter alia, stent thrombosis and major haemorrhage) and/or does not allow the subject to adhere to the requirements of the protocol.
3. Any SAE, clinically significant AE, severe laboratory abnormality, intercurrent illness, other medical condition, or change in the subject's condition which indicates to the Investigator that continued participation is not in the best interest of the subject for any reason, including ethics.
4. Females who become pregnant at any time during the study period must be discontinued immediately and counselled appropriately. The Investigator must follow the pregnancy to completion of term.
5. Requirement of prohibited concomitant medication.
6. Subject failure to comply with protocol requirements or study related procedures.
7. Termination of the study by the Sponsor or regulatory authorities.
8. When patients reach a primary endpoint or key safety endpoint (including but not limited to definite acute stent thrombosis, disabling stroke (modified Rankin score 2 at 90 days plus increase in 1 mRS category from the pre-stroke baseline)), the investigator needs to decide if study medication will be permanently discontinued, interrupted, modified or continued. In case of intracranial bleeding the protocol mandates stopping the study treatment.

If a subject withdraws from the study, the Investigator will complete and report the observations as thoroughly as possible up to the date of withdrawal including the date of last study medication dose and the reason for withdrawal.

If the subject is withdrawn due to an AE (including clinically relevant laboratory abnormalities); the Investigator will follow the subject until the AE has resolved, stabilised, or can be explained by reasons not attributable to the investigational product.

All subjects who are withdrawn from the study should complete protocol specified withdrawal procedures (Section 6.2.3 end of study).

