4.3.2. Withdrawal procedures

If the Investigator removes a subject from the study or if the subject withdraws consent for any reason after receiving the first dose, a complete set of Early Withdrawal visit should be carried out, preferably prior to the subject being placed on alternative therapy.

An Early Withdrawal Visit will include the same assessments and procedures as the end-of-treatment visit (section 6.2.3). Additionally, the date study medication was last taken will be recorded. The Investigator should start the subject on appropriate oral anticoagulant treatment (see section 5.3.) and the prescription should be recorded in the eCRF, if the information is available.

All results of evaluations and observations, pertinent to the study, together with a description of reason(s) for withdrawal must be recorded in the eCRF. If a subject is withdrawn from the study due to an AE, the event must be recorded on the AE page of the eCRF. Any additional study-specific procedures conducted due to the AE should be recorded on the eCRF as an unscheduled procedure. Any subject with an SAE or an AE that led to study medication discontinuation will be followed until the subject returns to baseline conditions or stabilises.

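### Section 4.3.1 directs that study participation be discontinued for items 2 to 6, against the protocol's rule that follow-up to month 12 ends only at the subject's own request

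*Combined protocol and SAP*

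**What the plan says.** **Text that ends participation.** The list in Section 4.3.1 opens with "Participation of a subject in this clinical study should be discontinued at all periods (except where noted) for any of the following reasons". Items 2 and 3 cover substantial risk and any adverse event, laboratory abnormality or illness that the investigator judges to make continuation unwise. Item 4 is pregnancy. Item 5 reads "Requirement of prohibited concomitant medication" and item 6 "Subject failure to comply with protocol requirements or study related procedures". The same section adds a general power: "The Investigator is also free to terminate a subject's involvement in the study at any time if the subject's clinical condition warrants it". Section 4.3.2 prescribes an Early Withdrawal Visit "If the Investigator removes a subject from the study or if the subject withdraws consent for any reason after receiving the first dose", so removal by the investigator is a route of its own, separate from withdrawal of consent.

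**Text that continues follow-up.** The synopsis (Study Duration) and Sections 3.1 and 5.7 say that clinical follow-up stops only when the subject explicitly asks. Section 6.5 keeps visits or calls going to month 12 after study drug is interrupted or stopped. Section 6.4 requires follow-up data to month 12 even when the subject was ineligible, was wrongly dosed, stopped treatment or refused on-site visits. Section 5.10.1 requires interruption of study medication during a prohibited drug and resumption after the course.

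**Analysis.** Section 11.4.1 analyses the first adjudicated major or clinically relevant non-major bleed (MCRB) up to Day 365 in the ITT set. Section 11.2 uses observed data without imputation and censors incomplete follow-up at the last known status.

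**The concern.** The two sets of instructions cannot both be followed. For a non-compliant subject, item 6 says participation should end, while Section 6.4 says data are collected to month 12. For a subject who needs a course of a prohibited drug, item 5 says participation should end, while Section 5.10.1 says interrupt and resume. No precedence rule is given, and nothing in Section 4.3 says that follow-up continues after removal by the investigator.

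A site that applied Section 4.3.1 literally could cause a subject without a prior MCRB to be censored at removal. Items 2 and 3 select on clinical condition, so that censoring may be informative. The trial is open-label and ASA is prohibited only in the edoxaban arm, so item 5, and possibly item 6, could act differently by arm. Removal after a first MCRB loses nothing for the primary endpoint, but it can still cut short the main efficacy endpoint, net clinical benefit and death.

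**Working it through.** **1. The texts side by side**

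| Situation | Section 4.3.1 | Elsewhere |
|---|---|---|
| Substantial risk; AE or illness (items 2, 3) | End participation | Follow-up ends only at the subject's request (synopsis, 3.1, 5.7); contacts continue after drug is stopped (6.5) |
| Pregnancy (item 4) | End participation | Same rule |
| Prohibited drug (item 5) | End participation | Interrupt, then resume (5.10.1) |
| Non-compliance (item 6) | End participation | Collect data to month 12 (6.4) |

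Items 1 (consent withdrawn) and 7 (study terminated) do not raise this conflict. Item 8 asks only for a study-medication decision.

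**2. Reproducing the design (Section 11.9)**

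Inputs from the protocol: one-year MCRB risk 24% (VKA) and 18% (edoxaban), two-sided alpha 0.05, 712 evaluable and 750 enrolled per arm.

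- Hazards: −ln(0.76) = 0.2744 and −ln(0.82) = 0.1985. HR = 0.1985/0.2744 = 0.7231; ln HR = −0.3242.
- Power = Φ(0.3242 × √(D/4) − 1.96), where D is the number of events.
- 712 per arm: D = 712 × (0.24 + 0.18) = 299.0, power 80.0%, as stated.
- 750 per arm: D = 750 × 0.42 = 315, power 82.0%.
- Reserve for loss to follow-up: (750 − 712)/750 = 5.1%.

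**3. Events lost if removal ends follow-up**

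Assumptions, not in the documents: a fraction e of each arm is removed, at a time U uniform over the year, and every removal ends follow-up.

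- Events lost per removed subject = F(1) − E[F(U)], with F(t) = 1 − exp(−λt). This is 0.1145 (VKA) and 0.0870 (edoxaban), sum 0.2015.
- Total lost = 750 × e × 0.2015.

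| e per arm | Events lost | Power |
|---|---|---|
| 2% | 3.0 | 81.7% |
| 5% | 7.6 | 81.1% |
| 10% | 15.1 | 80.1% |
| 20% | 30.2 | 78.1% |

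The margin of 315 − 299.0 = 16.0 events is used up at e = 15.96/(750 × 0.2015) = 10.6%. Earlier removal costs more: with all removals on Day 1, 5% leaves 315 × 0.95 = 299.2 events (80.1%) and 10% leaves 283.5 (77.9%).

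**4. Possible shift in the hazard ratio**

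Further assumption: after removal the bleeding hazard is m times the arm's own. Under this model, censoring at removal always gives 0.7231. The table shows what full follow-up would have given (large-sample limit of the Cox estimate, by numerical integration over one year).

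| Removed, edoxaban / VKA | m = 0.5 | m = 1 | m = 2 | m = 3 |
|---|---|---|---|---|
| 2% / 2% | 0.7232 | 0.7231 | 0.7233 | 0.7237 |
| 10% / 10% | 0.7233 | 0.7231 | 0.7238 | 0.7255 |
| 5% / 2% | 0.7178 | 0.7231 | 0.7330 | 0.7418 |
| 2% / 5% | 0.7287 | 0.7231 | 0.7139 | 0.7066 |

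With equal removal the shift is at most 0.7255 − 0.7231 = 0.0024. With unequal removal it is at most about 0.02, in either direction, and it is zero if removal leaves the hazard unchanged.

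**The case against.** The best counter-argument is that the authors meant drug discontinuation. Section 4.3 is headed "Removal of Subjects From Therapy". Item 8, under the same lead-in, speaks only of study medication. Section 6.3.1 treats withdrawals for adverse events under Section 4.3 as a kind of early anticoagulant discontinuation. Section 6.5.1 restricts loss to follow-up to failed contact at the final visit, and a note to the Schedule of Events asks subjects who stop study anticoagulant early to stay on the schedule. Harm therefore needs a site to follow Section 4.3 and overlook several more specific sections. This stands as evidence of intent and is why the effect is probably small. It does not change the operative words, which concern the study. Item 8 shows that the authors wrote study medication when they meant it.

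Four stronger readings are tempting and are not supported:

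- *That the Early Withdrawal Visit conflicts with the month-12 end-of-treatment visit.* Section 4.3.2 asks for it "preferably prior to the subject being placed on alternative therapy" but does not say that it replaces the month-12 visit, which Section 6.2.3 keeps on schedule. Both can be done.
- *That Section 4.3.1 limits data after removal by the investigator to the withdrawal date.* That sentence is written for a subject who withdraws. The duty to follow an adverse event to resolution likewise does not say that endpoint follow-up then stops.
- *That the 30-day adverse event window in Section 9.5.1 cuts off endpoint reporting.* The Schedule of Events notes call for endpoint reporting throughout the study, so no change is needed there.
- *That items 2 to 6 should become reasons to stop study drug.* Section 5.7 keeps subjects on the assigned regimen as far as possible. It also ties a stop for changed health status to a label contraindication. Simply swapping participation for study medication would make a missed visit a ground for stopping anticoagulation.

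**Conclusion.** The contradiction is real and can be seen by reading the sections together. The lead-in to Section 4.3.1 directs discontinuation of participation for items 2 to 6, and Sections 4.3.1 and 4.3.2 also let the investigator end involvement or remove a subject. The rest of the protocol reserves the end of follow-up to the subject. A reader might infer that the primary result is materially biased, but the documents give no removal rates and do not support that. Power stays above 80% up to about 10.6% removed per arm at uniform times. The hazard ratio shift of about 0.02 needs both unequal removal (5% against 2%) and a threefold hazard after removal. All removal rates, removal times and multipliers are assumptions. The point should be fixed because the instruction is wrong as written and cheap to correct, not because a large effect has been shown.

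**What to change.** Add to Sections 4.3.1 and 4.3.2 that:

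- withdrawal initiated by the investigator under items 2 to 6, or termination of involvement for clinical condition, concerns the assigned study medication only and does not end clinical follow-up;
- study drug is stopped, interrupted or resumed according to Sections 5.7 and 5.10.1, and items 2 to 6 create no grounds for stopping it beyond Section 5.7;
- endpoint follow-up continues on the scheduled contacts to Day 365 unless the subject limits or withdraws consent under Section 6.5 or the study is terminated;
- the Early Withdrawal Visit is additional to the month-12 visit in Section 6.2.3.

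The cost is amendment wording and a communication to sites. Contacts to month 12 are already scheduled for all subjects, so the follow-up schedule does not grow.

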4.3.2. Withdrawal procedures

If the Investigator removes a subject from the study or if the subject withdraws consent for any reason after receiving the first dose, a complete set of Early Withdrawal visit should be carried out, preferably prior to the subject being placed on alternative therapy.

An Early Withdrawal Visit will include the same assessments and procedures as the end-of-treatment visit (section 6.2.3). Additionally, the date study medication was last taken will be recorded. The Investigator should start the subject on appropriate oral anticoagulant treatment (see section 5.3.) and the prescription should be recorded in the eCRF, if the information is available.

All results of evaluations and observations, pertinent to the study, together with a description of reason(s) for withdrawal must be recorded in the eCRF. If a subject is withdrawn from the study due to an AE, the event must be recorded on the AE page of the eCRF. Any additional study-specific procedures conducted due to the AE should be recorded on the eCRF as an unscheduled procedure. Any subject with an SAE or an AE that led to study medication discontinuation will be followed until the subject returns to baseline conditions or stabilises.

4.3.3. Study or its terminations

If the Sponsor or their representatives, Investigator, or CA officials discover conditions during the study that indicate that the study or site involvement should be terminated. Conditions that may warrant termination of the study or involvement of a study site include, but are not limited to:

- The discovery of an unexpected, serious, or unacceptable risk to patients enrolled in the study.
- The decision on the part of the Sponsor to suspend or discontinue testing, evaluation, or development of the study drug.
- Failure of the Investigator(s) to comply with pertinent clinical trial regulations.
- Submission of knowingly false information from the research facility to the Sponsor, Clinical Monitor, or the Clinical Research Assistant.
- Insufficient adherence to protocol requirements
- Study termination and follow-up will be performed in accordance with applicable local regulations."

4.4 Subject Replacement

Not applicable.

4.5 Subject Re-screening Procedures

If during study qualification: _____

- a staged PCI is planned, eligibility is assessed after completion of the last stage of PCI

5. TREATMENT REGIMENS ADMINISTERED

5.i. Method of Assigning Subjects to-Treatment Regimens

After the IC has been signed and eligibility confirmed, the Investigator contacts the IXRS to assign an individual study identification number.

The Investigator should be prepared to provide subject information, including, but not limited to: age, body weight, clinical presentation [ACS or stable coronary artery disease (CAD)], CrCL using Cockcroft-Gault formula (see Section 17.6) and whether the subject is taking concomitant P-gp inhibitors requiring edoxaban dose reduction (according to local SmPC or 1B as applicable).

Randomization is stratified by clinical presentation (ACS or stable coronary disease), requirement for dose adjustment of edoxaban, and by geographical region (i.e. Latin America, Western Europe, Eastern Europe, Asia, as applicable).

Subjects will be assigned randomly via the above mentioned IXRS such that the study has a 1:1 ratio of subjects in the two antithrombotic treatment regimens.

The specifications for generation of the randomization schedule will be prepared by the study biostatistician and the IXRS vendor. An independent biostatistician, not otherwise part of the study team, will generate the randomization schedule. For this study, the randomization schedule refers to a list that includes the subject identification number (ID), randomization block number, and randomization treatment.

5.2. Study Treatment Regimens

5.2.1. Edoxaban-based regimen for 12 months

- Edoxaban 60 mg once-daily or 30 mg once-daily in selected subjects (see Section 5.3.1).
- Clopidogrel 75 mg once-daily (or in the presence of a documented clinical need prasugrel [5mg or 10 mg once-daily] or ticagrelor [90 mg twice-daily] may be used).
- The use of a P2Y₁₂ antagonist other than clopidogrel must be pre-declared.
- Concomitant use of another anti-platelet agent (i.e. ASA) is not allowed.

5.2.2. VKA-based regimen for 12 months (control regimen)

- Oral VKA of choice with dosing for target international normalized ratio (INR) between 2.0 - 3.0, inclusive.
- Clopidogrel 75mg once-daily (or in the presence of a documented clinical need prasugrel [10 mg once-daily]/ ticagrelor [90 mg twice-daily] may be used).
- ASA (100 mg once-daily) for a minimum of 1 month and up to 12 months duration at the Investigator discretion guided by the clinical presentation

(ACS or stable CAD), and upon the CHA2DS2-VASc and HAS-BLED score (1).

- The use of a P2Y₁₂ antagonist other than clopidogrel must be pre-declared, together with the intended duration of ASA treatment.

For simplicity, this protocol uses the term "edoxaban" to refer to edoxaban tosylate, "clopidogrel" to refer to clopidogrel bisulfate and the term "prasugrel" to refer to prasugrel hydrochloride.

Pre-declaration means that the Investigator specifies this information in the IXRS, prior to randomization and assignment to an antithrombotic regimen.

3. Edoxaban

Edoxaban tosylate (DU-176b, trade names Lixiana®, Savaysa®), referred throughout this protocol by the term "edoxaban" for simplicity, is part of the edoxaban-based regimen. Please refer to Section 5.9 Labeling and Packaging.

According to local SmPC or 1B as applicable, subjects may take edoxaban with or without food, in the morning or evening, but at approximately the same time every day.

If a dose of edoxaban is missed, the dose must be taken as soon as possible as long as on the same day. The dose of edoxaban must not be doubled to make up for a missed dose.

